## 9.4 STATISTICAL ANALYSES PLAN

### 9.4.1 GENERAL APPROACH

*Behavioral and brain data analysis will undergo separate analyzing streams to test intervention effects and underlying mechanisms at baseline and post-intervention. Given the scope of this 2-year R61 project, the logical first step at this early stage of research is to examine the potential intervention effects and mechanisms, then move to the full scale RCTs for R33 phase. To address our study Aims, repeated-measures ANOVA will be used. By utilizing all assessment points, this approach allows for well-powered tests to detect significant differences in changes across the experimental conditions, even when assuming smaller magnitude effect sizes. Effect size measures (from the repeated-measures ANOVA, Cohen's  $d$  highlighting mean differences between treatment and control groups across assessments) will also be calculated to describe the intervention's effect on study outcomes.*

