## 5.5 STRATEGIES FOR RECRUITMENT AND RETENTION

*We anticipate to enroll 70 participants (males and females) who are at least 18 years old across different race and ethnicity based on local demographic characteristics. Subjects will be recruited through print and media ads within local community. This will include radio and online ads and recruitment through social media. Flyers will be distributed throughout the local community. Based on our and other's previous experiences in longitudinal studies, about 5-10% of participants will dropout over the study period due to illness or relocation. We plan a dropout rate of 20% for this brief intervention given the population is polysubstance users. We propose to recruit 70 adults of which 56 (80%) will complete the study.*

*Compensation and Retention. Participants will be financially compensated with \$300 in total for completing the study protocol (approximately for 15 hours of time); participants who only partially complete the protocol will be compensated based on prorated hours. To maximize participant retention we will maintain contact with participants over time via frequent assessment intervals (e.g., requiring a functioning phone number and email address to contact participants by phone or email as needed, and obtaining the name, address, and phone number of at least 2 friends or classmates who can provide contact information for the participants, should we be unable to contact them during the study; emails and reminder phone calls prior to all study visits; offer flexible scheduling options for assessment (including weekends); provide fair compensation to participants; and maintain positive relations with participants. These procedures were used to maintain adequate participant retention in our prior NIH studies.*

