#### 9.2 SAMPLE SIZE DETERMINATION

*Our RCT design is focused on determining if within-person brain changes significantly differ across the intervention groups. All participants in this study will be those who use polysubstance. In prior work involving smokers (N = 27), we detected significant fMRI signal changes in the ACC/mPFC (Cohen's  $d = .90$ ) after 2-wk of IBMT than before IBMT . Compensating for the expected variability of findings in ACC/mPFC activity in polysubstance use, we thus expect a conservative, medium to large (Cohen's  $d = .80$ ) effect (i.e., we expect the effect size between the intervention and control conditions to be 0.80 at post-intervention) based on ours and other studies. However, we may expect polysubstance users to be somewhat more variable. Given the power considerations, we increased our sample size to 35 per group, which will give us 90% power to detect fMRI signal changes evoked by IBMT. The target sample size for the proposed study in the R61 phase (n = 70; 35/condition) is designed to provide sufficient evidence to detect significant brain changes in ATC users following interventions. Given we anticipate up to 20% attrition across the R61 phase of the study, power analysis suggests adequate power.*

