#### 9.3 POPULATIONS FOR ANALYSES

*The analysis population will be Modified Intention-to-Treat Analysis Population. Specifically, these participants are those who completed the full-dose of the intervention (10 sessions) and have completed data for the primary endpoint.*

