### 9.4.2 ANALYSIS OF THE PRIMARY ENDPOINT(S)

*The primary endpoints are brain assessments and are all repeated measures assessed at baseline and post-intervention. For brain assessment of brain assessment of functional activity, whole-brain analyses of fMRI timeseries during resting state will be calculated and for all endpoints based on standardized processing pipelines of fMRI data using REST software ([www.restfmri.net](http://www.restfmri.net)). After these data preprocessing and calculation, numerical values will be generated for each brain voxel. Next, the effects of intervention (IBMT vs. RT) on primary endpoints will be examined using repeated-measures ANOVA with time x group interaction effect. Threshold-free cluster enhancement approach will be used to identify clusters showing significant effects. Variance and covariance across repeated measures will be calculated as part of the ANOVA. Age and sex will be included as covariates to control for potential confounding effects of age and sex on brain outcomes. Results will be presented as F values for the interaction effect, along with p values to indicate statistical significance. Normality and homogeneity of variance assumptions will be checked using SPSS built-in tools for ANOVA. Multiple comparison corrections will be conducted using FDR correction. Missing data will be handled with case-wise deletion.*

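### Section 9.4.1 claims good power for effects smaller than planned; the documents do not support this, and for a medium effect it is untrue unless the baseline-to-post correlation is high

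*Combined protocol and SAP*

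**What the plan says.** Section 9.2 sizes the trial on one effect: "we expect the effect size between the intervention and control conditions to be 0.80 at post-intervention". On that basis "we increased our sample size to 35 per group, which will give us 90% power to detect fMRI signal changes evoked by IBMT". The same section describes the design as focused on "determining if within-person brain changes significantly differ across the intervention groups", so the contrast of interest is the arm difference in change. It then allows for dropout ("Given we anticipate up to 20% attrition across the R61 phase of the study") and concludes that power is adequate, without giving a figure. Section 5.5 gives the matching count: "We propose to recruit 70 adults of which 56 (80%) will complete the study".

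Section 9.3 restricts the analysis set to "those who completed the full-dose of the intervention (10 sessions) and have completed data for the primary endpoint", and section 9.4.2 adds "Missing data will be handled with case-wise deletion". Dropouts therefore leave the analysis altogether. Section 9.4.2 tests time x group on the baseline and post-intervention scans, voxel by voxel, with threshold-free cluster enhancement and FDR correction.

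Section 9.4.1 then says of using every assessment point that "this approach allows for well-powered tests to detect significant differences in changes across the experimental conditions, even when assuming smaller magnitude effect sizes".

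**The concern.** The only power figure in the plan is for d = 0.80. A two-group calculation with no allowance for dropout needs 34 of the 35 enrolled per arm to reach it. Section 9.4.1 goes further and says the tests remain well powered for smaller effects. It gives no effect size, power or correlation to support that.

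The sentence changes no test and no sample size, but it describes how sensitive the trial is. Someone who accepts it could take a non-significant interaction as evidence against a medium effect. If power for such an effect is near one half, that reading is unsafe.

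**Working it through.** **Inputs from the documents.** d = 0.80, 35 per arm and 90% power (9.2); 56 of 70 completing (5.5), which is 28 per arm if losses are balanced; completers only, with case-wise deletion (9.3, 9.4.2); two scans in the primary analysis (9.4.2).

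**Assumptions, because the plan is silent.** Alpha 0.05, two-sided, one test; equal SD in both arms and at both scans; no loss or gain from the age and sex covariates; baseline-to-post correlation ρ shown from 0.3 to 0.8. The value d = 0.5 is an example.

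**Method.** With two scans and two arms, the time x group test is a two-sample t-test on change scores. With n per arm, its degrees of freedom are 2n − 2 and its noncentrality is d × √(n/2), where d is on the change scale.

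**Step 1: reproduce the plan's figure.** n = 35, d = 0.80: noncentrality 0.80 × √17.5 = 3.347, 68 df, critical t 1.995, power 91.0%. This agrees with the stated 90%. The smallest n reaching 90% is 34 per arm. One-sided testing would give 95.2%, which does not match.

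**Step 2: the same calculation for smaller effects.** At n = 28 the noncentrality is d × √14, with 54 df and critical t 2.005.

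| d (change scale) | 35 per arm | 28 per arm |
|---|---|---|
| 0.8 | 91% | 84% |
| 0.7 | 82% | 73% |
| 0.6 | 70% | 60% |
| 0.5 | 54% | 45% |

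The smallest effect detectable at 35 per arm is 0.68 with 80% power and 0.79 with 90%. At 28 per arm it is 0.76 and 0.88.

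**Step 3: credit the repeated measures.** If d is the arm difference at post-intervention in raw SD units, as in 9.2, the change-scale effect is d / √(2(1 − ρ)). At ρ = 0.5 the divisor is 1, so the table in Step 2 applies unchanged. For d = 0.5:

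| ρ | change-scale d | 35 per arm | 28 per arm |
|---|---|---|---|
| 0.3 | 0.42 | 41% | 34% |
| 0.5 | 0.50 | 54% | 45% |
| 0.6 | 0.56 | 64% | 54% |
| 0.7 | 0.65 | 76% | 66% |
| 0.8 | 0.79 | 90% | 83% |

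The correlation needed for 80% power is ρ = 1 − (0.5/m)²/2, where m is the 80% detectable effect from Step 2. With m = 0.679 (35 per arm) this gives 0.729, and with m = 0.762 (28 per arm) it gives 0.785. These are about 0.73 and 0.79. Below ρ = 0.5, the change-score test has less power than a comparison of post-intervention values alone.

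**Step 4: multiplicity.** Every figure above is for one test. The whole-brain correction in 9.4.2 lowers power further. The documents do not contain what is needed to say by how much.

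**The case against.** The best defence is that section 9.4.1 defines neither well powered nor smaller, and that it appeals to a repeated-measures gain that can be real. Against an 80% standard there is some room: d = 0.7 has 82% power at 35 per arm, and at ρ = 0.8 a post-intervention d of 0.5 reaches 90% at 35 per arm and 83% at 28. This part of the defence stands. A reader might infer that the design has no margin at all below d = 0.80, but that is true only against the stated 90%. The defence does not rescue the sentence as written, because the plan states no correlation. At the 28 per arm it expects to analyse, even d = 0.7 on the change scale has only 73%.

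A second defence is the third scan in the schedule of activities. If the effect persisted fully and the test compared baseline with the mean of both later scans (equal correlations), d = 0.5 would have 56% power at 28 per arm and 66% at 35 for ρ = 0.5, and 78% and 87% for ρ = 0.7. However, the plan describes no follow-up profile, and 9.4.2 confines the primary analysis to baseline and post-intervention.

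One-sided testing would not help enough: d = 0.5 on the change scale would have 66% power at 35 per arm and 58% at 28.

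Two stronger readings go beyond the documents. A reader might infer that the step to the R33 phase depends on how a null result is read, but no section says so. 9.4.1 speaks of potential effects and commits to reporting effect sizes. A reader might also put a number on the power lost to voxelwise correction by using a strict per-test alpha, but neither threshold-free cluster enhancement nor FDR is a fixed per-test alpha.

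**Conclusion.** The assurance in 9.4.1 is unsupported. For a medium effect it is untrue unless the baseline-to-post correlation is high. On the basis that reproduces the plan's own 90%, d = 0.5 has 54% power at 35 per arm and 45% at 28. On the post-intervention scale it needs a correlation of about 0.73 (35 per arm) or 0.79 (28 per arm) to reach 80%. This rests on a two-sided 5% single test, balanced dropout, equal variances and d = 0.5 as the example.

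This is an unsupported statement about power, not an arithmetic error. The 90% in 9.2 reproduces at 35 per arm, and d = 0.80 still has 84% at 28. It does not follow that the sample size must change.

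**What to change.** In 9.4.1, delete the closing clause about smaller effect sizes.

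In 9.2, state the alpha and sidedness, whether d is on the change scale or is a post-intervention difference, and the assumed baseline-to-post correlation. Give the smallest detectable change-scale effect at the expected 28 per arm: 0.76 for 80% power and 0.88 for 90%, for a single two-sided 5% test before multiplicity correction. If a different alpha or sidedness is chosen, recompute these two values. Add one sentence saying that a non-significant result does not rule out a medium effect.

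The cost is a few sentences and a less favourable stated sensitivity. No participants, scans or procedures are added.

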### 9.4.2 ANALYSIS OF THE PRIMARY ENDPOINT(S)

*The primary endpoints are brain assessments and are all repeated measures assessed at baseline and post-intervention. For brain assessment of brain assessment of functional activity, whole-brain analyses of fMRI timeseries during resting state will be calculated and for all endpoints based on standardized processing pipelines of fMRI data using REST software ([www.restfmri.net](http://www.restfmri.net)). After these data preprocessing and calculation, numerical values will be generated for each brain voxel. Next, the effects of intervention (IBMT vs. RT) on primary endpoints will be examined using repeated-measures ANOVA with time x group interaction effect. Threshold-free cluster enhancement approach will be used to identify clusters showing significant effects. Variance and covariance across repeated measures will be calculated as part of the ANOVA. Age and sex will be included as covariates to control for potential confounding effects of age and sex on brain outcomes. Results will be presented as F values for the interaction effect, along with p values to indicate statistical significance. Normality and homogeneity of variance assumptions will be checked using SPSS built-in tools for ANOVA. Multiple comparison corrections will be conducted using FDR correction. Missing data will be handled with case-wise deletion.*

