### 3 OBJECTIVES AND ENDPOINTS

OBJECTIVES	ENDPOINTS	JUSTIFICATION FOR ENDPOINTS
Primary		
This study aims to investigate the modulation effects of a novel body-mind intervention on brain outcomes.	Baseline and post-intervention assessments of brain outcomes (functional activity in anterior cingulate cortex/medial prefrontal cortex).	The novel body-mind intervention should lead to improvement in brain outcomes at post-intervention compared to baseline.
Secondary		
N/A	N/A	N/A
Tertiary/Exploratory		
N/A	N/A	N/A

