### 9 STATISTICAL CONSIDERATIONS

#### 9.1 STATISTICAL HYPOTHESES

- Primary Endpoint(s):

We hypothesize that, compared to participants who receive a RT control intervention, participants who receive IBMT for improving brain outcomes will have improved anterior cingulate cortex/medial prefrontal cortex functional activity after completing the intervention at post-assessment. Alternatively, our null hypothesis is that there will be no difference in the effects of IBMT for improving brain outcomes and those of RT at post-assessment.

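### The primary hypothesis is about ACC/mPFC activity, but section 9.4.2 describes only a whole-brain voxelwise analysis, with no regional mask, summary or rule tying a result to that hypothesis

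*Combined protocol and SAP*

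**What the plan says.** Section 3 defines the only endpoint, the primary one, as "functional activity in anterior cingulate cortex/medial prefrontal cortex" at baseline and post-intervention. Section 9.1 hypothesises that, compared with relaxation training (RT), "participants who receive IBMT for improving brain outcomes will have improved anterior cingulate cortex/medial prefrontal cortex functional activity" at post-assessment; the null is no difference.

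Section 9.2 describes the design as testing whether "within-person brain changes significantly differ across the intervention groups". It cites an ACC/mPFC signal change of d = 0.90, after versus before IBMT, in 27 smokers, and then plans on a smaller value: "we expect the effect size between the intervention and control conditions to be 0.80 at post-intervention". With 35 per group, it continues, "which will give us 90% power to detect fMRI signal changes evoked by IBMT". Neither alpha nor sidedness is given.

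Section 9.4.2 is the only section that specifies the primary analysis. It says "whole-brain analyses of fMRI timeseries during resting state will be calculated and for all endpoints based on standardized processing pipelines of fMRI data". A value is produced at every voxel, the time by group interaction is tested by repeated-measures ANOVA with age and sex as covariates, TFCE identifies clusters, and FDR handles multiplicity. Section 9.4.1 adds a Cohen's d "highlighting mean differences between treatment and control groups across assessments", without naming a region. Sections 9.4.3 (secondary) and 9.4.9 (exploratory) are marked not applicable.

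Section 5.5 states: "We propose to recruit 70 adults of which 56 (80%) will complete the study".

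**The concern.** The region that defines success in sections 3 and 9.1 does not appear in section 9.4.2. Significance testing is planned, but nothing connects a significant voxel or cluster to the hypothesis. The ACC and mPFC have no single self-evident border. Without a fixed mask, someone must decide after seeing the map whether a cluster that straddles or adjoins the region counts, how much of it must lie inside, and which sign is an improvement. Two analysts given the same map could disagree on whether the null was rejected.

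The multiplicity wording does not settle this. Section 9.4.2 names both TFCE and FDR but does not say how they combine, over which family FDR is applied, or at what level. FDR applied over a whole map limits the expected share of false detections across that map. It does not fix the error rate of a claim about one region.

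There is one objective and no secondary endpoint, so the trial's confirmatory conclusion rests on this test. The power statement is affected as well, because the 90% is quoted for a comparison that section 9.4.2 does not define.

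**Working it through.** **Sections side by side**

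| Item | Sections 3, 9.1, 9.2 | Section 9.4.2 |
|---|---|---|
| Region | ACC/mPFC | Whole brain; ACC/mPFC not mentioned |
| Unit | Activity in that region | Each voxel |
| Measure | Functional activity | Resting-state fMRI; no measure named |
| Direction | Improved | Not defined |
| Error level | Not stated | FDR; level and family not stated |
| Regional test | Implied | None, and none in any other section |

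**Inputs for power.** From section 9.2: d = 0.80 between arms, 35 per arm, stated power 90%. From section 5.5: 56 completers. Section 4.4 defines completion as baseline, all 10 sessions and the post-intervention assessment, which is in substance the analysis population of section 9.3. Even dropout (assumed) gives 56 / 2 = 28 per arm. Alpha 0.05 two-sided is assumed.

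**Method.** Two-sample noncentral t, with noncentrality d × √(n/2) and 2n − 2 degrees of freedom.

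1. *The plan's own figure.* n = 35: 0.80 × √17.5 = 3.347, df 68, critical t 1.995, power **91.0%**. The stated 90% is reproduced as a single unadjusted comparison of one number per participant.

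2. *The same test in expected completers.* n = 28: 0.80 × √14 = 2.993, df 54, critical t 2.005, power **83.6%**. This takes d = 0.80 to apply to whatever scale is tested.

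3. *If d = 0.80 is on the post-score scale and change is tested.* With equal SDs at both visits and no baseline difference, d for change = 0.80 / √(2(1 − r)), where r is the pre-post correlation. Section 9.2 gives no r, so the values below are assumptions, at 28 per arm:
   - r = 0.3: d = 0.676, power 70%
   - r = 0.5: d = 0.800, power 84%
   - r = 0.7: d = 1.033, power 97%

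   Power reaches 90% only when r is about 0.59 or more.

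4. *Power of the voxelwise analysis.* This cannot be calculated. The documents give no threshold, search volume, smoothness or spatial extent of effect, and TFCE borrows strength from neighbouring voxels. Steps 1 to 3 contain no allowance for a voxel search, so none of them is the power of the analysis in section 9.4.2.

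**The case against.** The strongest reply is that section 9.4.2 can be read as a sequence: voxel values are computed first, and the ANOVA is then applied to the primary endpoint, which section 3 has already placed in the ACC/mPFC. Checking assumptions with SPSS, and a Cohen's d built on group means, fit extracted regional values better than a voxel map. That makes a regional intention plausible. It does not supply a mask, a summary or a measure, and TFCE works on a map rather than on one extracted number. An intention that the reader has to infer is not a prespecified test.

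Four stronger readings are tempting, and the documents do not support them:

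- *A cluster anywhere in the brain would count as success.* Sections 3 and 9.1 name the region, so a cluster clearly outside it would not meet the hypothesis. The gap is the boundary and the rule.
- *There is no inferential procedure.* Section 9.4.2 does specify F and p values, TFCE and FDR.
- *The voxelwise power is some particular low figure.* Any such figure needs a per-voxel threshold that the plan does not give.
- *The reported Cohen's d will be inflated by taking it from significant clusters.* Section 9.4.1 does not say where it is taken from.

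Nor is a one-sided basis for the 90% convincing. One-sided 0.05 at 28 per arm gives 90.5%, but section 9.2 attaches the 90% to 35 per group, where one-sided power would be 95.2%. The planned F test and the no-difference null also point to a two-sided test.

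Sections 9.4.1 and 9.4.7 describe early-stage pilot work. That tempers the consequences, but the trial still states a hypothesis, a null and a power, and section 9.4.1 presents it as the step before full-scale trials.

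**Conclusion.** The point stands and should be corrected. The endpoint and hypothesis concern one region, while the primary analysis as written covers the whole brain, and nothing in the plan fixes in advance how the second answers the first. This conclusion comes from the text and depends on no assumed number.

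The 90% belongs to a single unadjusted comparison with all 35 per arm. For a single regional test in the expected completers it is 83.6%, assuming two-sided 0.05, even dropout and d = 0.80 on the tested scale. If d = 0.80 refers to post-intervention scores and change is tested, power could be lower or higher than that, because section 9.2 gives no pre-post correlation. The 70% to 97% range shows that dependence; it does not measure the mismatch. How much power the voxelwise search gains or loses relative to 90% cannot be stated from the documents.

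**What to change.** In section 9.4.2:

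- Make the primary test the IBMT versus RT difference in change from baseline to post-intervention in one named resting-state measure, averaged over one ACC/mPFC mask. Test it once at two-sided 0.05, keeping age and sex as covariates.
- Fix the mask, the measure and the direction of improvement before any post-intervention imaging data are analysed.
- State that the hypothesis is met only if this test is significant in the stated direction.
- Take the reported effect size and confidence interval from the fixed mask.
- Keep the whole-brain TFCE map as a supporting or exploratory analysis, with one stated correction and its family of tests.

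In section 9.2, state alpha, sidedness and whether d = 0.80 is on the post-score or change scale, with the assumed pre-post correlation if one is needed. Restate power for this test at 28 completers per arm.

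The cost is plan wording and one mask extraction from scans already scheduled. There are real downsides. A focal effect may be diluted in a mask mean, effects outside the mask become supportive only, and the stated power may fall below 90%. Applying d = 0.80 to a mask mean is also an assumption, because section 9.2 does not say how the earlier d = 0.90 was extracted.

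### The primary time-by-group test on two scans is a change-score comparison; adding the baseline scan as a covariate would estimate the same arm difference more precisely for one degree of freedom

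*Combined protocol and SAP*

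**What the plan says.** Section 9.4.2 restricts the primary endpoint to the baseline and post-intervention scans. After preprocessing, "numerical values will be generated for each brain voxel", and "the effects of intervention (IBMT vs. RT) on primary endpoints will be examined using repeated-measures ANOVA with time x group interaction effect". On covariates it says: "Age and sex will be included as covariates to control for potential confounding effects of age and sex on brain outcomes". The baseline scan enters only as the first level of the time factor; no section lists it as a covariate. Results are to be reported as F and p values.

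Section 9.2 describes the design as "determining if within-person brain changes significantly differ across the intervention groups" and gives the target: "we expect the effect size between the intervention and control conditions to be 0.80 at post-intervention". It claims 90% power with 35 per group. Section 5.5 states: "We propose to recruit 70 adults of which 56 (80%) will complete the study". Section 9.3 limits the analysis set: "these participants are those who completed the full-dose of the intervention (10 sessions) and have completed data for the primary endpoint". Section 9.4.1 says: "By utilizing all assessment points, this approach allows for well-powered tests to detect significant differences in changes across the experimental conditions".

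**The concern.** A repeated-measures ANOVA with two time points tests the arm difference in post minus baseline. Subtracting baseline fixes its slope at 1. When the two scans are only moderately correlated, the true slope is below 1, and the subtraction adds baseline noise to every participant's outcome. A model that estimates the slope removes that noise.

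What is at stake is precision, not validity. The plan counts on a powerful test, expects to lose a fifth of its participants, and treats this phase as the step before full-scale trials. A wider interval than the collected data allow makes the result less useful for that purpose.

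**Working it through.** **Inputs from the documents.** Two scans in the primary analysis (Sections 3 and 9.4.2); age and sex as covariates (9.4.2); d = 0.80 and 35 per arm (9.2); 56 completers (5.5), so 28 per arm if equal.

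**Assumptions not in the documents.** Two-sided alpha 0.05; ρ of 0.3, 0.5 and 0.7; equal SDs at the two scans (varied under the objection); one summary value per person.

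**The plan's own figure.** For a two-group comparison at d = 0.80, the noncentrality is 0.80 × √(35/2) = 3.35. Power is 91.7% by the normal approximation and 91.0% by the t distribution, so the stated 90% is reproduced. At 28 per arm the noncentrality is 0.80 × √(28/2) = 2.99, and power is 84.9% (normal) or 83.6% (t).

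**Identity.** On one simulated data set without covariates, the time-by-group F was 2.8247 and the squared t on the change scores was 2.8247. With age and sex allowed to act on the change, the F is the squared t for arm in a regression of change on arm, age and sex.

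**Variances, in post-scan SD units, n = 28 per arm.**
- Planned: 2(1−ρ) × 2/n, residual df 56 − 4 = 52.
- Baseline-adjusted: (1−ρ²) × 2/n × (1 + 1/50), residual df 51. The last factor is the expected loss from chance baseline imbalance.
- Ratio before that loss: (1−ρ²)/[2(1−ρ)] = (1+ρ)/2. With the loss: 1.02 × (1+ρ)/2.

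At ρ = 0.5 the planned SE is √(1.0 × 2/28) = 0.267. The adjusted SE is √(0.75 × 2/28 × 1.02) = 0.234.

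| ρ | Variance ratio | 95% half-width, planned vs adjusted | Planned wider by | Power, d = 0.80 in post-scan SDs | Power, d = 0.80 in change-score SDs |
|---|---|---|---|---|---|
| 0.3 | 0.663 | 0.635 vs 0.517 | 23% | 70% vs 86% | 84% vs 95% |
| 0.5 | 0.765 | 0.536 vs 0.469 | 14% | 84% vs 92% | 84% vs 92% |
| 0.7 | 0.867 | 0.415 vs 0.387 | 7% | 97% vs 98% | 84% vs 88% |

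Two power columns are shown because Section 9.2 does not say which SD scales d. At ρ = 0.5, a variance ratio of 0.765 makes 56 completers worth about 56/0.765 = 73 under the planned test. With equal SDs, break-even is where 1.02 × (1+ρ)/2 = 1, that is ρ = 2/1.02 − 1 = 0.961.

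**Simulation** (6,000 trials per setting, 28 per arm, true difference 0.80, age and sex fitted). Mean estimates lay between 0.796 and 0.802 for both methods. Empirical SEs, planned vs adjusted, were 0.320 vs 0.264, 0.273 vs 0.236 and 0.208 vs 0.195 at ρ = 0.3, 0.5 and 0.7. Power was 69% vs 85%, 82% vs 91% and 96% vs 98%. Type I error at ρ = 0.5 was 4.7% for both.

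**The case against.** - **The planned test is valid and asks the question Section 9.2 poses.** This stands: it is an efficiency point in an early-phase study. It is not a reason to keep the less precise model, because regressing the change on arm plus baseline gives the same arm coefficient and t as regressing the post-intervention value on arm plus baseline. The within-person-change wording can therefore remain.
- **The primary analysis is whole-brain, voxelwise and corrected, and reports no interval.** This stands as a limit on the figures, which describe a single ACC/mPFC value. The variance argument still applies at each voxel.
- **ρ and the SD ratio are unknown.** This also stands. With a post-scan SD 1.25 times the baseline SD, the variance ratio including the slope cost is about 0.80, 0.91 and 1.00 at ρ = 0.3, 0.5 and 0.7, and 1.02 at ρ = 0.8, a slight loss. With an SD ratio of 0.8 the gain is larger: 0.50, 0.57 and 0.63 before the 2% slope cost. The possible loss is trivial and the possible gain is not.
- **The two estimates agree only if the arms are comparable at baseline.** Randomisation provides that, but the completer-only set in Section 9.3 and case-wise deletion may not preserve it. Under selective dropout the two estimates can diverge. That is a separate weakness, and baseline adjustment does not cure it.
- **Timing of the scan.** Section 4.1 assigns arms before the baseline assessment, and Section 1.3 puts the scan and the first intervention contact at the same visit. The scan is a proper covariate only if it precedes the first session. The term baseline implies this, but the plan could say so.
- **A Day 90 scan exists (Section 1.3), and Section 9.4.1 could be read to include it.** Sections 3 and 9.4.2 fix the primary comparison at two scans, so the identity applies to the analysis as specified.

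**Conclusion.** The point holds as a recommended improvement, not as an error. The primary test is a change-score comparison that leaves the baseline scan unused as a covariate. For a single ACC/mPFC value at 28 per arm with equal SDs, baseline adjustment removes about 34%, 24% and 13% of the variance of the arm difference at ρ = 0.3, 0.5 and 0.7 (one minus the tabulated ratios). The gain is large if scan-to-scan correlation is low and negligible if it is high. That the adjusted model is generally at least as precise is well founded. The size of the gain is illustrative, because the documents give neither ρ nor the SD ratio.

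**What to change.** In Section 9.4.2, make the primary voxelwise model the Day 31 value regressed on arm, that voxel's own baseline value, age and sex. Keep the planned threshold-free cluster enhancement and multiplicity correction. If the change is preferred as the outcome, add the baseline value to that model; the arm test is identical.

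Alongside F and p, report the adjusted Day 31 arm difference with a 95% confidence interval for an ACC/mPFC summary whose mask is fixed before the data are seen. State that the baseline scan is taken before the first session. State also that baseline adjustment does not correct selection from the completer-only set or from case-wise deletion. In Section 9.4.1, reword the references to the assessments used so that they name the baseline and post-intervention scans only.

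The cost is one residual degree of freedom (52 to 51 at 56 completers), a covariate that differs by voxel, and the work of defining the mask. The documents do not say whether the chosen software supports such a covariate, so this needs checking first. No new data are needed, since the baseline scan is already in the schedule.
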